7.2 Secondary outcomes

For the secondary outcome analyses, results will be used from both eyes to investigate if atropine has an effect on the following endpoints at month 24; central axial length, pupil diameter, uniocular BCdVA and uniocular near VA. Each of these endpoints will be compared between the atropine and placebo groups using GEE and 95% CIs and will be adjusted for the corresponding baseline secondary outcomes (if available).

For the following endpoints at month 24; binocular BCdVA, binocular near VA, reading speed, and quality of life (i.e. EQ-5D-Y VAS and Index) comparisons between the atropine and placebo groups will be performed using analysis of covariance (ANCOVA) and 95% CIs and will be adjusted for the corresponding baseline secondary outcome (if available). Tolerability at month 24 will be compared between the atropine and placebo groups using an independent samples t-test. Spectacle correction at month 24 will be compared between the atropine and placebo groups using the chi-square test (or Fisher's exact test if appropriate). N(%) of spectacle correction (all day and sometimes) will also be presented by treatment arm.

The number of AEs, ARs, SAE, SARs, SUSARs and number (%) of patients experiencing these events will be reported. The chi-square test (or Fisher's exact test if appropriate) will be used to check whether incidences of adverse events differ between the treatment groups. Risk ratio and 95% CIs will be reported.

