1.3 Study Objectives

The primary objective is:

 To evaluate the efficacy of 0.01% atropine eye drops to reduce the progression of myopia in children after 24 months of treatment.

The secondary objectives are:

- To evaluate the safety and tolerability of low dose atropine eye drops in terms of difficulties with near vision and reading, local discomfort and stinging of eye drops, photophobia, and occurrence of allergic reactions.
- To determine the mechanism of action of atropine eye drops. Specifically, we will evaluate if atropine has an effect on central axial length of the eye, position of the lens, peripheral retinal defocus and use of spectacle correction.

The exploratory objectives are:

• To explore the influence of other factors in the progression of myopia, including accommodation, chorio-retinal thickness at the macula, peripheral axial length, hours of outdoor activity, iris colour, ethnicity, and family history.

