1.4 Inclusion and Exclusion Criteria

Patients will be eligible to participate in the study if they fulfil the following criteria below. Eligibility will be confirmed by a medically qualified doctor and documented on the eligibility checklist form.

Inclusion Criteria

- 1. Age 6-12 years (at the time of consenting)
- 2. Myopia of -0.5D or greater (spherical equivalent refractive error) in both eyes
- 3. Best-corrected distance visual acuity (BCDVA) 0.20 logMAR or better in both eyes

Exclusion Criteria

- 1. Children with other ocular morbidities
- 2. Myopia of -10D or greater in either eye
- 3. Astigmatism of 2D or higher in either eye
- 4. Amblyopia
- Significant health problems that can compromise the ability to attend research visits or complete the trial
- 6. Other factors that may compromise the ability to attend the research appointments
- 7. Parents or children with poor understanding of the English language
- 8. Children enrolled in other interventional trials*
- 9. Allergy or hypersensitivity to atropine or excipients
- 10. Previous use of atropine eye-drops, prior or current use of Ortho-K contact lenses or contact lenses with dual focus, multifocal or extended depth of focus lens design
- 11. Children or Parents / Guardians with latex allergy as the dropper used to administer the eye-drop contains latex

*Children enrolled in observational studies are potential candidates for CHAMP UK. Whether or not children enrolled in CHAMP UK are also involved in other observational studies is at the discretion of the CHAMP UK local Principal Investigator (PI) and should be considered when the burden on participants is not expected to be onerous. Coenrolment with other studies should be documented in the Case Report Form (CRF).

Full details of the background to the trial and its design are presented in the protocol.

Doc No: ST06-RD01 Page **6** of **47**

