8.3 Baseline Characteristics

- Minimisation factors, n (%) by treatment arm and total
- Gender, n (%) by treatment arm and total
- Age (years), mean (SD) by treatment arm and total
- Weight (kg), mean (SD) by treatment arm and total
- Height (cm), mean (SD) by treatment arm and total
- Ethnicity, no. (%) by treatment arm and total
- Parental myopia, no. (%) by treatment arm and total
- SER in both eyes, mean (SD) by treatment arm and total
- SER in left eye, mean (SD) by treatment arm and total
- SER in right eye, mean (SD) by treatment arm and total
- Central axial length in both eyes, mean (SD) by treatment arm and total
- Central axial length in left eye, mean (SD) by treatment arm and total
- Central axial length in right eye, mean (SD) by treatment arm and total
- EQ5D-Y- Visual Analogue Scale, mean (SD) by treatment arm and total
- EQ5D-Y- index score, mean (SD) by treatment arm and total
- Uniocular BCdVA in both eyes, mean (SD) by treatment arm and total
- Uniocular BCdVA in left eye, mean (SD) by treatment arm and total
- Uniocular BCdVA in right eye, mean (SD) by treatment arm and total
- Binocular BCdVA, mean (SD) by treatment arm and total
- Uniocular near VA in both eyes, mean (SD) by treatment arm and total
- Uniocular near VA in left eye, mean (SD) by treatment arm and total
- Uniocular near VA in right eye, mean (SD) by treatment arm and total
- Binocular near VA, mean (SD) by treatment arm and total
- · Reading speed, mean (SD) by treatment arm and total
- Pupil diameter in both eyes, mean (SD) by treatment arm and total
- Pupil diameter in left eve. mean (SD) by treatment arm and total
- Pupil diameter in right eye, mean (SD) by treatment arm and total
- Spectacle correction, no. (%) by treatment arm and total
- Frequency of spectacle correction; all day and sometimes, no. (%) by treatment arm and total
- Contact lens use, no. (%) by treatment arm and total
- Frequency of contact lens use; all day and sometimes, no. (%) by treatment arm and total

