8.5 Trial Outcomes

Primary efficacy outcome:

 SER at month 24: mean (SD) by treatment arm, difference in means with 95% CI, p-value from GEE model, adjusted for baseline SER in ITT analysis and PP analysis.

Secondary analysis of the primary efficacy outcome:

- SER at month 24: mean (SD) by treatment arm, difference in means with 95% CI, p-value from GEE model, adjusted for baseline SER, minimisation variables (i.e. site and ethnicity), baseline age and history of parental myopia (at least one parent), in ITT analysis and PP analysis.
- Uniocular (BCdVA) at month 24: mean (SD) by treatment arm, difference in means with 95% CI, p-value from GEE, adjusted for baseline uniocular BCdVA in ITT and PP analysis.
- Binocular BCdVA at month 24: mean (SD) by treatment arm, difference in means with 95% CI,
 p-value from ANCOVA, adjusted for baseline BCdVA in ITT and PP analysis.
- Central axial length at month 24: mean (SD) by treatment arm, difference in means with 95% CI,
 p-value from GEE, adjusted for baseline central axial length in ITT and PP analysis.
- Uniocular near VA at month 24: mean (SD) by treatment arm, difference in means with 95% CI, p-value from GEE, adjusted for baseline uniocular near VA in ITT and PP analysis.
- Binocular near VA at month 24: mean (SD) by treatment arm, difference in means with 95% CI, p-value from ANCOVA, adjusted for baseline binocular near VA in in ITT and PP analysis..
- Pupil diameter at month 24: mean (SD) by treatment arm, difference in means with 95% CI, p-value from GEE, adjusted for baseline pupil diameter in ITT and PP analysis.
- Spectacle correction at month 24: no. (%) by treatment arm, risk difference and p-value from from chi-square test in ITT and PP analysis.
- Frequency of spectacle correction at month 24 (all day and sometimes): no. (%) by treatment arm in ITT and PP analysis.
- EQ-5D-Y VAS at month 24: mean (SD) by treatment arm, difference in means with 95% CI, p-value from ANCOVA, adjusted for baseline EQ-5D-Y VAS in intention to treat analysis and per protocol analysis.
- EQ-5D-Y Index score at month 24: mean (SD) by treatment arm, difference in means with 95% CI, p-value from ANCOVA, adjusted for baseline EQ-5D-Y index in ITT and PP analysis.
- Tolerability eye feels at month 24: mean (SD) by treatment arm, difference in means with 95% CI, p-value from independent t-test, in ITT and PP analysis.

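### Use of spectacle correction is tested at month 24 only as an unadjusted yes/no, although a graded measure and baseline values are collected; the yes/no is likely to be near its ceiling for much of the myopia range, and contact lens wear is left undefined

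*Supplement*

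**What the plan says.** - **Objective.** SAP section 1.3 includes among the mechanisms to be evaluated "position of the lens, peripheral retinal defocus and use of spectacle correction". Section 2.2 lists spectacle correction as a secondary outcome.
- **Test.** Section 7.2: "Spectacle correction at month 24 will be compared between the atropine and placebo groups using the chi-square test", with Fisher's exact test as the alternative. Section 8.5 asks for "Spectacle correction at month 24: no. (%) by treatment arm, risk difference and p-value from" the chi-square test. The main outcomes table shell leaves the adjusted columns blank for this endpoint.
- **Graded use.** Section 7.2: "N(%) of spectacle correction (all day and sometimes) will also be presented by treatment arm". Section 8.5 repeats this: "Frequency of spectacle correction at month 24 (all day and sometimes): no. (%) by treatment arm in ITT and PP analysis". The shell leaves the difference and p-value cells empty.
- **Baseline.** Section 8.3 summarises spectacle correction and its frequency at baseline. Section 7.2 adjusts the GEE and ANCOVA endpoints for their baseline value where available. Tolerability is left unadjusted for a stated reason, that it has no baseline measurement. Spectacle correction has a baseline and is still unadjusted.
- **Contact lenses.** Section 8.3 lists contact lens use and "Frequency of contact lens use; all day and sometimes, no. (%) by treatment arm and total". No item in sections 7, 8.5 or 8.8, and no outcome table, carries contact lens use into follow-up. Exclusion criterion 10 bars Ortho-K and special-design lenses; ordinary contact lenses are not mentioned.
- **Population.** Section 1.4 requires "Myopia of -0.5D or greater (spherical equivalent refractive error) in both eyes". Section 5 assumes mean control progression of -0.8D over 24 months, a 40% reduction on atropine, and an SD of 0.7D.

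**The concern.** A yes/no variable can show a treatment effect only if a reasonable share of children could answer either way. Eligibility guarantees myopia in both eyes, and the plan expects it to worsen on average. Many children may therefore wear spectacles at month 24 in either arm, whatever atropine does. What could more plausibly move is how much they wear them, and that is collected but not compared. Leaving out the baseline category also gives up precision that the SAP takes for its other repeatedly measured secondary endpoints.

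The second issue is definition. Spectacles and contact lenses are separate yes/no items in the baseline shell, and no rule says how a child corrected only by contact lenses is classified at follow-up. If that child counts as No, the tested variable mixes uncorrected children with fully corrected ones.

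At stake is the interpretation of one secondary objective: a null result could be read as no effect on spectacle use when the test could hardly have found one.

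**Working it through.** **Numbers of children.** The SAP gives no power figure for this endpoint, so I first reproduced the one it gives for the primary outcome. With a difference of 0.32D, SD 0.7D, two-sided 5% (sidedness assumed), 90% power and 2:1 allocation:

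- Control eyes = (1 + 1/2) × (1.960 + 1.282)² × 0.7² / 0.32² = 75.4, so 76, with 152 on atropine, as stated.
- (76 + 152) × 1.9 / 2 = 216.6 children; 216.6 / 0.75 = 288.8, so 289, as stated.
- Completers at 15% dropout: 193 × 0.85 = 164 atropine and 96 × 0.85 = 82 placebo.

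**Where the ceiling lies.** Assume, because the documents give no rule, that a child wears correction if SER at month 24 is -0.5D or worse. Take the section 5 progression (placebo -0.80D; atropine 0.6 × -0.80 = -0.48D; SD 0.7D in both arms) as normal and unrelated to entry SER. For entry SER *b*, the proportion corrected is Φ((-0.5 - b + 0.80)/0.7) on placebo and Φ((-0.5 - b + 0.48)/0.7) on atropine. Power treats all 246 children as entering at *b* (normal approximation).

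| Entry SER | Placebo | Atropine | Difference (points) | Power |
|---|---|---|---|---|
| -0.5D | 87.4% | 75.4% | 12.0 | 60% |
| -1.0D | 96.8% | 91.9% | 4.9 | 29% |
| -1.5D | 99.5% | 98.3% | 1.2 | 8% |
| -2.0D | 99.95% | 99.8% | 0.2 | 2% |
| -3.0D | 100% | 100% | 0 | <1% |

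From about -1.5D the yes/no variable has almost nothing to detect, even if atropine works exactly as assumed. Near -0.5D it does have something to detect. The approximation flatters the sparse rows: exact enumeration of the chi-square test at -1.5D gives about 1%, not 8%.

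**Power at assumed wear rates** (atropine v placebo, 164 v 82, exact enumeration, two-sided 5%):

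| Rates | Chi-square | Fisher |
|---|---|---|
| 97% v 99% | 5.7% | 2.8% |
| 95% v 99% | 30% | 22% |

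Fisher is the relevant column when few children answer No: at a 3% No rate the expected placebo count is 0.03 × 82 = 2.5.

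**Contact lenses.** Suppose every child is fully corrected, some wear contact lenses only, and these count as No. Contact-lens-only wear of 10% on placebo and 5% on atropine then appears as 90% v 95% spectacle wear and is significant about 33% of the time; 15% v 5% is significant about 73% of the time. These rates are assumptions, and the calculation applies only if the coding works this way.

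**The case against.** The strongest reply is that the ceiling is not in the documents. They give no wear rate and no baseline SER distribution; being myopic is not the same as wearing spectacles, and the shells provide No and Sometimes categories at baseline. This stands as a limit on the claim. The ceiling is an inference that is strong from about -1.5D at entry and weak near -0.5D.

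Second, an unadjusted comparison of randomised arms is unbiased, so omitting baseline is a matter of efficiency. That is correct, but the data are already collected and the gain costs only wording.

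Third, the benefit of the graded analysis cannot be sized from the documents. All-day wear of 60% v 75%, for example, would have about 66% power, but that 15-point difference is chosen, not derived. The case for the grading is that it has room to vary, not that a particular power is secured.

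Fourth, section 3.5 leaves coding to the CRF, which is not shown and may already handle contact lens wearers. The point is therefore that the SAP does not define the classification, not that children will be misclassified.

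A reader might also infer that one or two contact lens switchers would change the result. In general they would not. Seven No answers would be expected to split about 5 v 2 (atropine v placebo), Fisher p = 1.0; two more on placebo (5 v 4) give p = 0.49, and two more on atropine (7 v 2) give p = 0.72. Only splits already weighted towards placebo lie near the threshold: 2 v 5 gives p = 0.043 and 3 v 4 gives p = 0.23.

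**Conclusion.** The point holds as a cheap improvement to a secondary analysis. The SAP tests the less informative form of the outcome, without the baseline it has collected, and leaves contact lens wear undefined. On assumed near-ceiling rates of 97% v 99% to 95% v 99%, power is roughly 6% to 30% by chi-square and 3% to 22% by Fisher. These figures rest on assumed wear rates and 15% dropout; the ceiling table also rests on the assumed -0.5D cut and on normal progression.

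Three stronger readings are not supported:

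- That the objective cannot be answered at all: the yes/no test keeps some power if many children enter near -0.5D, and the graded data will be shown by arm.
- That every child is progressing: -0.8D is a mean, and with an SD of 0.7D about 13% of placebo children (1 - Φ(0.80/0.7)) and 25% of atropine children (1 - Φ(0.48/0.7)) would show no progression.
- That the No answers are mainly contact lens wearers with the opposite meaning: no contact lens rate is given.

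The primary conclusion is unaffected.

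**What to change.** In sections 7.2 and 8.5, compare the arms at month 24 on the ordered category none / sometimes / all day, using a proportional-odds model adjusted for the baseline category and reporting an odds ratio with 95% CI. In 7.5 and 8.8, use the repeated-measures counterpart for months 6, 12 and 18. Keep the yes/no table and risk difference as descriptive, and amend the outcome table shells to match. State in advance what is done if very few children fall in none, for example a baseline-adjusted logistic model of all-day wear against the rest.

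Count contact lens wear as correction where follow-up data exist. Where they do not, state that No may include contact lens wearers.

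The cost is SAP wording and one derived variable, with no new data needed for the spectacle part. The downside is a proportional-odds assumption and an effect measure that is less direct than a risk difference.

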2.2 Secondary outcome measures

- Central axial length: measured using a laser biometer at central fixation conditions
- Best corrected distance visual acuity (BCdVA) (uniocular and binocular): assessed using the logMAR ETDRS chart. This is a standard letter chart used in research to ensure accuracy and validity of the acuity measurements and has been shown to be repeatable in children
- Near visual acuity (VA) (uniocular and binocular): tested using near logMAR ETDRS at 40 cm
- Reading speed: measured with the Wilkins Rate of Reading test
- Pupil diameter: measured using an autorefractor
- Spectacle correction
- Tolerability: using a 4-point scale to quantify, from the point of view of the participant, (1) local irritation/stinging associated with eye drop instillation;
 - (2) photophobia; and
 - (3) difficulties reading and writing
- Adverse event rates and allergic reactions rates
- Quality of Life: measured using the EQ-5D-Y

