5. SAMPLE SIZE CALCULATIONS

We anticipate that the effect of atropine eye drops in a UK population will be smaller than the reported effect in Chinese populations, but assuming that atropine reduces the progression of myopia by at least 40% in 24 months from a control mean of -0.8D7 (40% of 0.8 is equivalent to a mean difference of -0.32D between intervention and control group at 24 months), using SD=0.7D, a correlation (interclass correlation coefficient) between eyes of 0.9 and a variation inflation factor of 1.9, we will need 97 participants in each group. Considering a dropout rate of 15% and that 10% of the recruited children will be Chinese, we will need a total of 289 participants: 193 atropine, 96 placebo (152 atropine, 76 placebo inflated by a variance inflation factor of 1.9) to detect this difference in the non-Chinese population with 90% power.

Justification: In a study of 400 Chinese children evaluating the effect of 24 months of 1% atropine eye drops, myopia progression was -1.20 +/- 0.69 D in the placebo control group, and -0.28 +/- 0.92 D in the atropine group. We have assumed that progression of myopia and efficacy of atropine will be less in UK children than in Chinese children2.

Progression of myopia of untreated children was estimated from the control groups of randomized controlled trials for myopia. The following progression data have been reported:

- Katz 2003⁴ (Chinese race): progression of -1.28D (SD 0.78) D after 2 years (control was spectacles)
- Edwards 2002⁵ (Chinese race): progression of -1.26D (SD 0.74) D after 2 years (control was single vision lenses)
- Chua 2006³, ATOM study (Chinese race): progression of -1.20D (SD 0.69) after 2 years (control was placebo drops)
- Hyman 2005⁶, COMET trial (children of mixed races, with whites being the most common ethnicity): progression of 1.32D after 3 years (standard error 0.04) (control was single vision lenses)
- Breslin 2013⁷, In an observational study from the UK, myopia progression was 1.14D after 3 years.

Doc No: ST06-RD01 Page **12** of **47**

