Doc No: ST06-RD01 Page **13** of **47**

7. **ANALYSIS PRINCIPLES**

Baseline characteristics and follow up measurements will be summarised as mean and standard deviation (SD), median and inter-quartile range (IQR) or numbers and frequencies (%) as appropriate, depending on the scale of measurement and distribution. Analysis will be based on both the intention to treat (ITT) principle and per protocol (PP) analysis. PP analysis will explore results in those who had at least 80% adherence to the study drug. A p-value <0.05 will be considered as statistically significant.

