8.10 Toxicity/ Symptoms

- AEs, no.events (%) by treatment arm, no. patients(%) by treatment arm, Risk ratio with 95% CI and p value
- ARs, no.events (%) by treatment arm, no. patients(%) by treatment arm, Risk ratio with 95% CI and p value
- SARs, no. events (%) by treatment arm, no. patients (%) by treatment arm, Risk ratio with 95% CI and p value
- UARs, no. events (%) by treatment arm, no. patients (%) by treatment arm, Risk ratio with 95% CI and p value
- SAEs, no. events (%) by treatment arm, no. patients (%) by treatment arm, Risk ratio with 95% CI and p value
- SUSARs, no. events (%) by treatment arm, no. patients (%) by treatment arm, Risk ratio with 95% CI and p value

Fatal AEs/SAEs, no. events (%) by treatment arm, no. patients (%) by treatment arm, Risk ratio with 95% CI and p value

AEs, ARs, SAEs, SARs, UARs and SUSARs will also be presented by system organ class.

Doc No: ST06-RD01 Page **21** of **47**

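### Adverse events are named as rates, but the arms are formally compared only on children with at least one event; repeat events and unequal observation time do not enter the comparison

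*Supplement*

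**What the plan says.** - **Outcome.** SAP section 2.2 names "Adverse event rates and allergic reactions rates". Neither that section nor the definitions in section 4 say whether a rate is a proportion of children or events per unit of time.
- **Description.** Section 7.2: "The number of AEs, ARs, SAE, SARs, SUSARs and number (%) of patients experiencing these events will be reported".
- **Comparison.** Section 7.2: "The chi-square test (or Fisher's exact test if appropriate) will be used to check whether incidences of adverse events differ between the treatment groups", followed by "Risk ratio and 95% CIs will be reported".
- **Output.** The first line of section 8.10 reads "AEs, no.events (%) by treatment arm, no. patients(%) by treatment arm, Risk ratio with 95% CI and p value". The same pattern is repeated for reactions, unexpected reactions, serious events, serious reactions, SUSARs and fatal events, and "AEs, ARs, SAEs, SARs, UARs and SUSARs will also be presented by system organ class".
- **Table shells (Appendix 1).** In the safety tables the risk ratio and p-value stand in the block for number of patients. The block for number of events has a count and a percentage per arm, and no ratio, interval or test.
- **Exposure.** Section 8.4 tabulates adherence, reasons for terminating study drug and premature withdrawals by arm. None of these is linked to the safety denominators. Child-years, an offset and a rate ratio appear nowhere in section 7.2, section 8.10 or the safety shells.

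**The concern.** Over two years in children, common adverse events recur. When most children in both arms have had at least one, the proportion with any event nears its ceiling: the risk ratio moves towards 1 and further events in the same child add nothing to the test. The event counts hold that information, but as laid out they cannot be interpreted. Allocation is 2:1, so with equal rates atropine supplies about two thirds of all events. If the percentage is a share of all events, a neutral result looks like an excess; if it is per child, it can exceed 100%. The shell does not say which.

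A child seen for 6 months without an event also counts the same as one seen for 24 months. If withdrawal differs between arms, the per-child risk differs even when the event rates do not. At stake is the sensitivity of one part of the safety assessment, the comparison of common adverse events.

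**Working it through.** **Inputs from the SAP.** 193 atropine and 96 placebo (sections 5 and 6.1); 24 months, with adverse events recorded at 6, 12, 18 and 24 months (section 3.3); significance at 0.05 (section 7), taken as two-sided. The arm sizes come from the refraction calculation and reproduce: (152 + 76) eyes × 1.9 / 2 = 216.6 children; 216.6 / 0.75 (15% dropout plus 10% Chinese) = 288.8, so 289. The plan gives no power or event rate for safety, so there is no safety figure to reproduce.

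**Assumptions.** Placebo rate r per child-year; true rate ratio 1.3 (2 for rarer events); between-child overdispersion k = 0 (Poisson), 0.5 or 1.0; full follow-up in the power comparison.

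**Formulas.** Mean count per child: m_P = 2r, m_A = 2r × rate ratio.
- Ever-event probability: 1 − exp(−m) if k = 0, otherwise 1 − (1 + km)^(−1/k).
- Per-child power: Φ[(p_A − p_P − 1.96·SE0)/SE1], with SE0 pooled and SE1 unpooled.
- Rate power: Φ[ln(rate ratio)/SE − 1.96], with SE² = (1/m_A + k)/193 + (1/m_P + k)/96.

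**Worked case: r = 1, rate ratio 1.3, k = 0.**
- m_P = 2.0 and m_A = 2.6, so p_P = 0.865, p_A = 0.926 and the risk ratio is 1.07.
- Per child: SE0 = 0.0366, SE1 = 0.0397; (0.0611 − 0.0716)/0.0397 = −0.27; power 40%.
- Rate: SE = √(1/501.8 + 1/192) = 0.0849; 0.2624/0.0849 − 1.96 = 1.13; power 87%.

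**Results.**

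| Placebo rate per child-year | Rate ratio | k | Ever-event, placebo v atropine | Risk ratio | Power, per child | Power, rate |
|---|---|---|---|---|---|---|
| 1.0 | 1.3 | 0 | 86.5% v 92.6% | 1.07 | 40% | 87% |
| 1.0 | 1.3 | 0.5 | 75.0% v 81.1% | 1.08 | 23% | 57% |
| 1.0 | 1.3 | 1.0 | 66.7% v 72.2% | 1.08 | 17% | 41% |
| 0.5 | 1.3 | 0 | 63.2% v 72.7% | 1.15 | 38% | 59% |
| 0.5 | 1.3 | 0.5 | 55.6% v 63.3% | 1.14 | 24% | 42% |
| 0.5 | 1.3 | 1.0 | 50.0% v 56.5% | 1.13 | 18% | 33% |
| 0.1 | 1.3 | 0 | 18.1% v 22.9% | 1.26 | 14% | 16% |
| 0.1 | 2 | 0.5 | 17.4% v 30.6% | 1.76 | 68% | 73% |
| 0.05 | 2 | 0.5 | 9.3% v 17.4% | 1.87 | 44% | 46% |

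**Unequal observation, no true difference (Poisson).** Suppose 15% of atropine and 5% of placebo children are observed for 6 months only. The split is illustrative: the SAP gives a single 15% dropout figure, not by arm.
- r = 1: 0.85 × 0.865 + 0.15 × 0.393 = 0.794, against 0.95 × 0.865 + 0.05 × 0.393 = 0.841; risk ratio 0.94.
- r = 0.5: 0.571 against 0.612; 0.93.
- r = 0.25: 0.352 against 0.380; 0.93.

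**Event share.** With equal rates and equal follow-up, atropine contributes 193/289 = 67% of events.

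**The case against.** The strongest case against has five parts.

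- **Repeat events are in the tables.** The sentence before the test requires event counts by arm, and the shells set them beside the patient counts. This stands. A reader might infer that the plan discards repeat events or that an excess would be concealed; the documents do not support that. Repeats are shown, but without person-time or a comparison.
- **A rate may mean a proportion.** The term is undefined, section 1.3 speaks of the occurrence of allergic reactions, and section 7.2 of incidences. This is a fair reading, so the plan does not clearly contradict itself. Under it, unequal observation time still matters.
- **The loss is confined to common events.** The comparison is repeated for reactions, serious categories and organ classes, where a drug effect may concentrate and the ceiling is remote. This stands: the two methods nearly coincide at low rates, so nothing here argues for changing the tests in sparse categories.
- **Stopping drops is not leaving follow-up.** Section 7 includes an intention-to-treat analysis, and section 6.2 keeps an unmasked child who discontinues drops on the trial. It is tempting to infer that early stopping on atropine would by itself make the drug look safer; that does not follow. The bias needs differential withdrawal from observation, which section 8.4 would reveal by arm.
- **Safety does not rest on this test alone.** Tolerability, near acuity, reading speed and pupil diameter are separate outcomes. One should not infer that the whole safety aim hangs on the per-child comparison.

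Count models also depend on how recurrent or ongoing events are split. That is a real cost, and such rules may sit in the protocol, which is not shown.

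**Conclusion.** The point holds in limited form. An outcome worded as a rate is compared only by children with at least one event. The event counts carry an undefined percentage in a 2:1 trial, and observation time is not used.

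For common events the loss is material. At an assumed 1 event per child-year and a true rate ratio of 1.3, power is 17–40% per child against 41–87% for a rate comparison; at 0.5 per child-year it is 18–38% against 33–59%. At about 0.1 per child-year or below there is little to choose. A risk ratio of 0.93–0.94 from unequal observation alone needs withdrawal to be higher on atropine, and the split used is illustrative.

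The event rates, the rate ratio and the overdispersion are all assumptions; the documents give none. The finding supports adding a rate comparison. It does not show that the risk ratio must be demoted, since which of the two leads is a matter of preference.

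**What to change.** In section 7.2, section 8.10 and the safety shells:

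1. Define the adverse event rate and the observation period over which events are counted.
2. Replace the event percentage with number of events and child-years of observation by arm.
3. For any adverse event, and for adverse reactions if they prove common, add a rate ratio with 95% CI from negative binomial regression, or Poisson regression with robust variance, using log observation time as offset. Place it beside the existing per-child risk ratio.
4. Keep the present per-child or exact tests for serious events, serious reactions, SUSARs and sparse organ classes.
5. State how ongoing and recurrent events are counted.

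The cost is SAP wording, one extra model per common class and the counting convention. The start and withdrawal dates needed for child-years should already be held.

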1. BACKGROUND AND DESIGN

Atropine 1% is very effective in slowing myopia progression, but it is not popular because of its unwanted side effects of pupillary dilation and cycloplegia and possible rebound effect. Atropine eye drops at a concentration of 0.01% are expected to be safe and well tolerated. This is supported by evidence from other trials that have employed the same and other more potent anti-muscarinic agents (e.g. 1% atropine; pirenzepine), and the well-established safety profile of atropine use in ophthalmology.

This is a multicentre, randomised, double-masked, placebo-controlled, superiority trial, with 2:1 allocation of intervention and control (atropine: placebo).

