1.2 Study Aim

The aim of the study is to evaluate the efficacy and safety of low dose atropine (0.01%) eye drops to reduce progression of myopia in UK children.

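### Adverse-event rows carry a p-value and a risk ratio but no risk difference, so rows with no placebo events have no usable interval for the excess risk

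*Supplement*

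**What the plan says.** The study aim (SAP 1.2) is to "evaluate the efficacy and safety of low dose atropine (0.01%) eye drops", so safety is part of the aim. Section 1.3 makes safety and tolerability a secondary objective.

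For adverse events, section 7.2 asks for numbers of events, numbers and percentages of patients, and a chi-square test (Fisher's exact where appropriate) that "will be used to check whether incidences of adverse events differ between the treatment groups". It adds: "Risk ratio and 95% CIs will be reported". Section 8.10 applies the same outputs to AEs, ARs, SARs, UARs, SAEs, SUSARs and fatal events, for example "SUSARs, no. events (%) by treatment arm, no. patients (%) by treatment arm, Risk ratio with 95% CI and p value". It also asks for presentation by system organ class, and the shells in Appendix 1 carry a risk ratio and p-value column on every such row. Section 7 sets the general threshold: "A p-value <0.05 will be considered as statistically significant".

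For harms, no section gives a risk difference, a method for zero cells, or guidance on reading a non-significant row. For spectacle correction, also a binary outcome, section 8.5 and footnote e of the main outcomes shell do plan a risk difference.

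**The concern.** The trial is sized for refraction, not for harms, and the 2:1 allocation leaves 96 placebo children. Two consequences follow for uncommon events. The test will often be non-significant when a real excess exists. In addition, the one planned effect measure fails in the sparsest rows: a ratio with a zero denominator has no finite estimate or upper limit.

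Serious, unexpected and organ-class rows are the likeliest to be sparse. There the reader would see counts, percentages and a p-value, but no statement of how large an excess on atropine remains compatible with the data. For a treatment given to children over 24 months, that upper limit is the information the safety aim needs. The trial can supply it, but the plan does not ask for it.

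**Working it through.** **Inputs from the documents.** Allocation is "with 2:1 allocation of intervention and control (atropine: placebo" (section 1). The sample size is "we will need a total of 289 participants: 193 atropine, 96 placebo" (section 5). The significance level is 0.05 (section 7), taken as two-sided. Section 5 assumes 15% dropout. Adverse-event rates are not given, so those below are assumptions.

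**The plan's own sample size.** It is driven by refraction: "40% of 0.8 is equivalent to a mean difference of -0.32D between intervention and control group at 24 months", with SD 0.7 D and 90% power. At 2:1, placebo n = (1 + 1/2) × (1.960 + 1.282)² × (0.7/0.32)² = 1.5 × 10.51 × 4.785 = 75.4, so 76, with 152 on atropine. Then (76 + 152) × 1.9/2 = 216.6, and 216.6/(1 − 0.15 − 0.10) = 288.8, so 289. The stated figure is reproduced. No harm rate enters it.

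**Power of the planned test.** All outcomes of 193 and 96 binomial trials were enumerated exactly. Fisher's test was used when any expected count was below 5 and the uncorrected chi-square otherwise, at two-sided 0.05. Only results with atropine worse were counted.

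| Placebo | Atropine | Power |
|---|---|---|
| 0% | 3% | 13% |
| 0% | 5% | 63% |
| 1% | 3% | 5% |
| 1% | 5% | 31% |
| 2% | 6% | 26% |
| 2% | 8% | 53% |
| 2% | 10% | 76% |
| 5% | 10% | 28% |
| 10% | 20% | 59% |

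With 15% dropout (about 164 and 82), power at 1% versus 5% falls to 22%.

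**With no placebo events.** For k/193 versus 0/96, Fisher's p is 0.100 at k = 7, 0.056 at k = 8 and 0.032 at k = 9. Nine affected children (9/193 = 4.7%) are therefore needed for p < 0.05.

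**How often a zero cell arises.** P(no placebo event) = (1 − p)^96, which is 38% at p = 1% and 14% at p = 2%. At 0.5% versus 1%, P(at least one arm has none) = 0.618 + 0.144 − 0.618 × 0.144 = 67%.

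**What the risk ratio gives then.** For 6/193 versus 0/96 the score interval runs from 0.79 to infinity. Adding 0.5 to each cell gives (6.5/194)/(0.5/97) = 6.5 with limits 0.37 to 114, which depend heavily on the arbitrary 0.5.

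**What a risk difference gives.** The Newcombe interval is built from the Wilson limits (l, u) of each arm:

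- lower = d − √[(p₁ − l₁)² + (u₂ − p₂)²]
- upper = d + √[(u₁ − p₁)² + (p₂ − l₂)²]

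For 7/193 versus 0/96, d = 3.63%. The Wilson limits are 1.77% to 7.30% on atropine and 0 to 3.85% on placebo.

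- lower = 3.63 − √(1.86² + 3.85²) = −0.6%
- upper = 3.63 + √(3.67² + 0²) = +7.3%

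So where Fisher gives p = 0.10, an excess of up to about 7 percentage points is not excluded. For 6 versus 0 the interval is −1.1% to +6.6%, and for 8 versus 0 it is −0.2% to +8.0%. For 0 versus 0 the upper limit is 1.96²/(193 + 1.96²) = 2.0%.

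**The case against.** A reader might infer that the plan makes non-significance its verdict on safety. The documents do not support that: section 7 sets a general threshold, and no passage says that p ≥ 0.05 will be read as safe. The protocol is not available here, so how safety conclusions are framed there cannot be judged.

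Nor is this the only assessment of harm. Near visual acuity, reading speed, pupil diameter and six tolerability items have their own estimates with 95% CIs, and the DMC monitors safety (9.2). Nor is the p-value all that survives in a zero-event row: events, patients and percentages by arm are always shown, so the difference itself can be worked out by hand. Where both arms have events, the planned risk ratio interval already shows whether a several-fold excess is compatible with the data.

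It would also go too far to say that the test misses most relevant excesses. The documents give neither rates nor a definition of relevant, and power is 53% to 76% at 0% versus 5%, 2% versus 8% and 2% versus 10%. Low power for rare harms is normal in a trial sized for efficacy: 80% power at 1% versus 3% would need about 611 placebo and 1,222 atropine children, and no SAP wording changes that.

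All of this stands and limits the point to adverse-event incidence. It leaves the reporting gap: zero-event rows have no planned interval that bounds the excess risk.

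**Conclusion.** The point holds as a specification gap in the adverse-event tables and is a cheap improvement. It is not evidence that the plan will declare safety from a non-significant test.

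That the risk ratio is undefined or unbounded when placebo has no events is arithmetic and needs no assumption. How often this happens, and the power figures, rest on assumed event rates, two-sided testing, the expected-count rule for choosing Fisher's test, and the full planned 193 and 96. Dropout makes both somewhat worse. The risk difference interval exists in every row, including those with no events in either arm, and the plan already uses a risk difference for spectacle correction.

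**What to change.** In sections 7.2 and 8.10, and in both safety shells of Appendix 1 (overall and by system organ class), add the risk difference, atropine minus placebo, in the proportion of patients affected, with a 95% score-type CI. Name one method in advance, Newcombe or Miettinen-Nurminen. Keep the risk ratio where both arms have events and mark it as not estimable otherwise. Add a sentence that the safety conclusion will quote the upper 95% limit of the excess risk for ARs and SAEs and will not rest on p ≥ 0.05.

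The cost is SAP wording and one column in two shells, with no new data or participants. The downside is a less favourable statement: with 7 versus 0 events, for example, the report would say that an excess of up to about 7 percentage points is not excluded, rather than only that the difference was not significant.

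Ranking the risk difference as the main safety measure, and dropping the organ-class p-values or labelling them descriptive, are optional preferences.
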